#### 8.2.4.5 Severity

Severity refers to the accumulated intensity of discomfort/impairment of health since the last recording of AEs. The Investigator will rate the intensity, seriousness, and causality

of the AEs. To achieve maximum consistency in the assessment of severity of adverse/medical events, it is recommended that National Cancer Institute (NCI) Common Terminology Criteria for Adverse Events (CTCAE) scale be used whenever possible, to assist the Investigator in determining the severity of adverse/medical event. Severity of adverse/medical events will be reported on the eCRF as mild, moderate, or severe according to the definitions provided below. Grading based on the CTCAE scale will not be entered into the eCRFs.

Severity	Corresponding NCI CTCAE Grade
Mild: awareness of a sign or symptom but easily tolerated	1
Moderate: discomfort sufficient to cause interference with normal daily activities	2
Severe: resulting in inability to do work or perform normal daily activities	3-5

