#### 8.2.4.6 Serious Adverse Event

An SAE is any adverse event occurring at any dose that results in any of the following outcomes:

- 1) Death
- 2) A life-threatening adverse event
- 3) Inpatient hospitalization or prolongation of existing hospitalization
- 4) A persistent or significant disability or incapacity
- 5) A congenital anomaly in the offspring of a patient who received the study treatment
- 6) Important medical events that may not result in death, be life-threatening, or require hospitalization but which in the Investigator's judgement may jeopardize the patient and may require medical or surgical intervention to prevent one of the outcomes listed in this definition. Examples of such medical events include allergic bronchospasm requiring intensive treatment in an emergency room or at home, blood dyscrasias or convulsions that do not result in inpatient hospitalization, or the development of drug dependency or treatment-related substance abuse.

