#### 8.2.4.9 Adverse Event of Special Interest – Neutropenia (Definitions and Management)

##### **Definitions**

*Mild Neutropenia:* A confirmed ANC  $\geq 1.0 \times 10^9/L$  and  $< 1.5 \times 10^9/L$ .

*Moderate Neutropenia:* A confirmed ANC  $\geq 0.5 \times 10^9/L$  and  $< 1.0 \times 10^9/L$ .

*Severe Neutropenia/Agranulocytosis:* A confirmed ANC  $< 0.5 \times 10^9/L$ .

An absolute neutrophil count (ANC) is confirmed as being less than a specified value if two consecutive counts (maximum 3 days apart) are both less than the specified value. If both consecutive counts are below  $1.5 \times 10^9/L$  but not in the same severity category of neutropenia, a third count will be required to determine the severity.

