8.1 Adverse Events

A summary table of adverse events will include the following information:

- number of patients exposed to study treatment
- number of patients experiencing at least one AE
- number of patients experiencing at least one severe AE
- number of patients experiencing at least one serious AE
- number of patients experiencing at least one drug-related AE
- number of deaths
- total number of patients withdrawn (and reason for withdrawal)
- number of withdrawals due to an AE

Adverse events will be coded using MedDRA. Adverse events are defined as AEs that occurred or worsened (increased in severity and/or frequency) on or after the first dose of study medication. Serious adverse events (SAEs) that occurred within 14 days after treatment discontinuation will be considered to be SAEs. Serious adverse events that occurred within 30 days after treatment discontinuation will be included in the database.

Adverse events will be summarized by treatment group using the total number of AEs and total exposure to the treatment, the total number and percent of patients who experience an AE, and the number and percent of patients who experienced an AE within each SOC (and preferred term within an SOC). AEs will also be presented by severity (mild, moderate, severe), by seriousness (serious, non-serious) and by relationship to study medication (at least possibly related, not related). The number of patients withdrawn will also be presented.

To count the number of patients who experienced each AE, patients who experienced the same AE multiple times will only be counted once for the corresponding preferred term. Similarly, if a patient experiences multiple AEs within the same SOC, that patient will be counted only once for that SOC. AEs will be tabulated presenting the SOC alphabetically, and within each SOC, preferred terms will be presented in decreasing order of the total number of patients who experienced each AE. In summaries presenting the

incidence of AEs by severity, seriousness, and relation to study medication, a patient with multiple events coded to a given preferred term or SOC will be counted once for that preferred term or SOC according to the most severe event, the most serious event, or the event with the closest relationship to study medication.

A listing of serious adverse events and a listing of withdrawals due to AEs will be presented. Patient deaths will be listed separately and discussed with patient narratives.

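### Neutropenia is graded by ANC in protocol 8.2.4.9 but by tolerance and daily function on the eCRF, so a symptom-free agranulocytosis can, though need not, be summarised as a mild AE

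*Protocol*

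**What the plan says.** **ANC scale.** Under Definitions in protocol 8.2.4.9, a confirmed ANC of 1.0 to below 1.5 x 10^9/L is mild neutropenia, 0.5 to below 1.0 is moderate, and below 0.5 is severe neutropenia or agranulocytosis. Confirmation takes two consecutive counts at most 3 days apart. If both are low but not "in the same severity category of neutropenia, a third count will be required to determine the severity".

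**eCRF scale.** Protocol 8.2.4.5 covers all AEs: "Severity of adverse/medical events will be reported on the eCRF as mild, moderate, or severe according to the definitions provided below". "Severity refers to the accumulated intensity of discomfort/impairment of health since the last recording of AEs". Mild is "awareness of a sign or symptom but easily tolerated"; severe is "resulting in inability to do work or perform normal daily activities". A second column, headed "Corresponding NCI CTCAE Grade", pairs mild with grade 1, moderate with grade 2 and severe with grades 3 to 5. CTCAE is recommended where possible to help the investigator, and its grade is not recorded on the eCRF.

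**Outputs.** SAP 8.1 summarises the "number of patients experiencing at least one severe AE" and promises a presentation of AEs as mild, moderate or severe. The shell for Table 14.3.1.1 compares the severe-AE count between arms with a p-value. SAP 8.5 leaves unscheduled laboratory results out of the summary tables and categorises laboratory results as low, normal or high.

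**The concern.** The same three words carry two meanings, and neither section refers to the other. The label that decides how the protocol manages a neutropenia is set by the count. The label that reaches the AE tables is set by the investigator's reading of a functional definition, with CTCAE as an optional aid. A low count without infection may cause no symptoms, so the two labels can disagree most where the count is lowest.

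Protocol 1.2 names agranulocytosis as the most significant serious event with deferiprone, and 8.2.4.9 makes neutropenia the event of special interest. At stake is whether the severity summaries in an open-label trial show the depth of neutropenia or differences in how sites read the scale.

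**Working it through.** The plan gives no figure on this point, so the check is mainly a comparison of the texts.

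**Step 1. The two scales applied to one case:** a confirmed ANC below 0.5 x 10^9/L with no symptoms.

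| Route | Resulting label |
|---|---|
| 8.2.4.9, by ANC | severe |
| 8.2.4.5, definitions read literally | mild is the nearest description |
| 8.2.4.5, CTCAE grade and crosswalk | depends on the CTCAE grade; the documents do not reproduce its neutrophil cut-offs |

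All three labels are consistent with the text. No rule says which one governs the eCRF entry for neutropenia, and the entry does not show which route was used.

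**Step 2. Does another planned summary give the ANC class?**

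- *ANC by visit (SAP 14.3.6.1 shells):* mean, SD, minimum and maximum. A minimum can reveal a very low scheduled count, but not how many patients had one or whether it was confirmed.
- *ANC shift tables:* low, normal or high at baseline against the last assessment. Counts of 0.4 and 1.4 could both fall under low, and a patient followed to recovery can end as normal.
- *ANC figure:* the proportion abnormal at each assessment, with no depth.
- *Unscheduled counts:* listed only (SAP 8.5). Routine hematology is weekly to Week 26 and biweekly after that. A confirming count within 3 days, and the every-2-day or daily follow-up in 8.2.4.9, will mostly fall outside that schedule.
- *Withdrawals:* agranulocytosis requires withdrawal (protocol 4.5), but so does mild or moderate neutropenia that has not resolved after 14 days (8.2.4.9). Withdrawal alone does not identify the class.
- *Preferred terms:* protocol 1.2 reports neutropenia, agranulocytosis and neutrophil count decreased separately. The term is a useful guide to depth but not a substitute for the class.
- *AE by severity:* promised in SAP 8.1, but neither the table list nor the shells contain such a table.

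**Step 3. How many patients are exposed?** Inputs: pooled incidence 1.7% for agranulocytosis and 6.2% for neutropenia (protocol 1.2); 142 deferiprone patients at the interim (SAP sample-size text); 200 at full size (2/3 x 300).

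Expected cases = n x p; chance of at least one = 1 - (1 - p)^n.

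- Agranulocytosis, n = 142: 142 x 0.017 = 2.4; 1 - 0.983^142 = 0.91.
- Agranulocytosis, n = 200: 200 x 0.017 = 3.4; 1 - 0.983^200 = 0.97.
- Neutropenia: 142 x 0.062 = 8.8; 200 x 0.062 = 12.4.

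The same formula gives 0.9865 and 0.8824 for 213 patients at 2% and 1%, against the SAP's stated 98% and 88%.

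**The case against.** The strongest reply is that 8.2.4.5 is not purely a symptom scale. It defines severity as discomfort or impairment of health, recommends CTCAE and prints a crosswalk that leads to severe. This stands. A reader might infer that a symptom-free agranulocytosis is at most mild on the eCRF. The text does not require that; it only leaves it open.

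The second reply is that the risk is not hidden. AEs are tabulated by preferred term whatever their severity, confirmed agranulocytosis forces withdrawal, and clinical actions follow the ANC class and not the eCRF entry. This also stands. A reader might further infer that the grading cannot be checked because the CTCAE grade is not stored. That does not follow, since the ANC values are in the hematology and local-laboratory listings.

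Two other readings are tempting. One is that a moderate neutropenia during a disabling illness would be graded severe. That merges two events: the illness is its own AE, and nothing in 8.2.4.5 transfers its functional effect to the neutropenia. The other is that seriousness has the same gap and needs an automatic rule. Protocol 8.2.4.6 already names "blood dyscrasias or convulsions that do not result in inpatient hospitalization" among its examples of important medical events, and 8.2.4.7 requires every SAE to reach the sponsor within 24 hours. Investigator judgement remains, but an automatic rule would be a preference and not the repair of a contradiction.

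Last, a patient drops out of the severe-AE count only if the neutropenia is under-graded and the patient has no other severe AE. This is correct and limits the effect. It does not remove the gap, because no planned summary reports the ANC class of the event of special interest.

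**Conclusion.** The point holds in limited form. Two unlinked scales share the same labels, and the one that feeds the severity summaries does not have to follow the ANC. Misgrading is possible, not inevitable. It would affect the by-severity presentation and the severe-AE count. It would not affect the preferred-term tables, the listings or the primary endpoint.

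About 2.4 agranulocytosis cases among 142 deferiprone patients, or 3.4 among 200, are exposed. This assumes that the pooled rate carries over, although protocol 1.4 says the earlier experience is predominantly in thalassemia. The documents give no basis for estimating how many cases would be misgraded. With so few expected, one or two would visibly change a severity row. The change is worth making because it replaces a judgement-based label for the drug's main risk with an objective one at little cost.

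**What to change.** **SAP 8.1.** For neutropenia, agranulocytosis and neutrophil count decreased, in both arms, derive severity from the lowest confirmed ANC class in protocol 8.2.4.9, using scheduled, unscheduled and local-laboratory counts. Use the derived severity in the severe-AE count and the by-severity presentation. Keep the eCRF entry, flagged, where no confirmed class exists.

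**SAP tables.** Add a table of confirmed neutropenia by ANC class and arm, and the by-severity AE table that SAP 8.1 promises. Because the repeat-count instructions in 8.2.4.9 are written for patients receiving deferiprone, show the lowest single count by class beside the confirmed class, so that a difference in confirmation between arms can be seen.

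**Protocol 8.2.4.5.** Add one sentence stating how the eCRF severity of neutropenia relates to the classes in 8.2.4.9. No clinical management changes.

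**Cost.** A small derivation from data already collected, and possibly a slightly higher count of severe AEs. The derivation also covers the 213 patients projected to have completed or withdrawn by the interim cut-off. The protocol sentence can help only the 17 ongoing patients and any enrolled later, so the SAP change matters more.

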#### 8.2.4.6 Serious Adverse Event

An SAE is any adverse event occurring at any dose that results in any of the following outcomes:

- 1) Death
- 2) A life-threatening adverse event
- 3) Inpatient hospitalization or prolongation of existing hospitalization
- 4) A persistent or significant disability or incapacity
- 5) A congenital anomaly in the offspring of a patient who received the study treatment
- 6) Important medical events that may not result in death, be life-threatening, or require hospitalization but which in the Investigator's judgement may jeopardize the patient and may require medical or surgical intervention to prevent one of the outcomes listed in this definition. Examples of such medical events include allergic bronchospasm requiring intensive treatment in an emergency room or at home, blood dyscrasias or convulsions that do not result in inpatient hospitalization, or the development of drug dependency or treatment-related substance abuse.

#### Clarifications:

- “Life-threatening” means that the patient was, in the view of the Investigator, at immediate risk of death from the event as it occurred. This definition does not include an event that, had it occurred in a more severe form, might have caused death.

- Hospitalization for elective treatment of a pre-existing condition that did not worsen during the study is not considered an AE.
- Complications that occur during hospitalization are AEs. If a complication prolongs hospitalization, the event is an SAE.
- “Inpatient” hospitalization means the patient has been formally admitted to a hospital for medical reasons. This may or may not be overnight. It does not include presentation at a casualty or emergency room unless the event meets one of the other criteria for being a serious adverse event.
- With regard to the criteria in (6) above, medical and scientific judgement should be used in deciding whether prompt reporting is appropriate in this situation.

#### 8.2.4.7 Procedures for Serious Adverse Event Reporting

Patients will be instructed to report SAEs to the Investigator immediately (**within 24 hours**) by telephone. The Investigator must report all SAEs to the Sponsor **within 24 hours** of occurrence or notification by the patient. These events must be faxed to the Sponsor using the Sponsor’s standard SAE form. The Sponsor will provide a list of project contacts for SAE receipt, fax numbers and telephone numbers.

The Investigator will always provide an assessment of causality at the time of the initial report.

A follow-up SAE form must be completed by the responsible Investigator/delegate and faxed to the Sponsor **within 5 calendar days**. Furthermore, as additional relevant follow-up information becomes available, the Investigator must complete a follow-up SAE form and fax it to the Sponsor.

The Sponsor will submit serious adverse drug events to the appropriate regulatory agencies, in line with local regulatory requirements and timelines.

Investigators must also report all SAEs to their respective IRB/IEC responsible for the study. The Sponsor will promptly inform all other sites of SAEs occurring at a single site that are at least possibly related to the study medication and are unexpected. All site Investigators will report these events to their IRB/IEC following the same timelines as above or following local IRB/IEC policy, whichever takes precedence.

#### 8.2.4.8 Follow-up and Documenting of SAEs

SAEs that occur during the study and for 30 days after the patient takes the last dose of study medication must be documented in the patient’s medical record and on the SAE Report form. A separate SAE Report form should be used for each SAE. The Investigator should attempt to establish a diagnosis of the event based on signs, symptoms, and/or other clinical information. In such cases, the diagnosis and not the individual signs/symptoms should be documented as the SAE.

All SAEs must be followed until resolution, until the condition stabilizes, until the event is otherwise explained, or until the patient is lost to follow-up. The Investigator is responsible to ensure that follow-up includes any supplemental investigations as may be

indicated to elucidate as completely as practical the nature and/or causality of the SAE. This may include additional laboratory tests or investigations, histopathological examinations, or consultation with other health care professionals.

The Sponsor may request that the Investigator perform or arrange for the conduct of supplemental measurements and/or evaluations. If a patient dies during participation in the study or during a recognized follow-up period, the Sponsor should be provided with a copy of any post-mortem findings, including histopathology. New or updated information should be recorded on the originally completed SAE page, with all changes signed and dated by the Investigator.

The CRA will verify the original SAE Report form against the source documents at the next monitoring visit.

#### 8.2.4.9 Adverse Event of Special Interest – Neutropenia (Definitions and Management)

##### **Definitions**

*Mild Neutropenia:* A confirmed ANC  $\geq 1.0 \times 10^9/L$  and  $< 1.5 \times 10^9/L$ .

*Moderate Neutropenia:* A confirmed ANC  $\geq 0.5 \times 10^9/L$  and  $< 1.0 \times 10^9/L$ .

*Severe Neutropenia/Agranulocytosis:* A confirmed ANC  $< 0.5 \times 10^9/L$ .

An absolute neutrophil count (ANC) is confirmed as being less than a specified value if two consecutive counts (maximum 3 days apart) are both less than the specified value. If both consecutive counts are below  $1.5 \times 10^9/L$  but not in the same severity category of neutropenia, a third count will be required to determine the severity.

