### 2.2 Secondary Objectives

The secondary objectives are:

- To evaluate the effect of deferiprone vs. deferoxamine on the patients' quality of life;
- To evaluate the safety and tolerability of deferiprone vs. deferoxamine.

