## 4.6 Treatment Interruptions

Study medication will be interrupted for **ANY** of the following reasons:

- If the patient develops an infection during the study, deferiprone must be interrupted immediately and neutrophil count should be obtained and monitored more frequently (every 2 days if ANC  $<1.5 \times 10^9/L$ ). Patients should be advised to report immediately to their physician any symptoms indicative of infection such as fever, sore throat, and flu-like symptoms. They will be provided with a thermometer, and instructed to seek immediate medical attention at a hospital or clinic if they experience fever (temperature  $>38.0^{\circ}C/100.4^{\circ}F$ ). Body temperature may be measured at the mouth, axilla, or ear. Patients/legal guardians will be provided with an emergency services card with contact information, and will be advised to carry this card at all times. In presence of confirmed fever and/or infection, patients will be required to have their neutrophil counts tested as soon as possible and no later than 24 hours after the symptoms of infection are detected. Therapy with deferiprone can be re-initiated once all symptoms have been resolved and it is deemed safe by the Investigator.
- If temperature is  $>38.0^{\circ}C/100.4^{\circ}F$  and ANC is  $\leq 0.5 \times 10^9/L$ , the following must be done:
  - Commence therapy with antibiotics immediately (treatment should depend on the site of the suspected infection and on local antibiotic policy)
  - Perform a chest x-ray, and collect blood and other relevant cultures (if possible, collect culture samples before initiating antibiotics)
- If the patient develops moderate neutropenia while on deferiprone (refer to [Section 8.2.4.9](#) for definition), therapy must be interrupted immediately and neutrophil count must be obtained and monitored every 2 days. Therapy with deferiprone can be re-initiated once two successive ANCs are  $>1.5 \times 10^9/L$  and it is deemed safe by the Investigator. The patient will be withdrawn from the study if the ANC remains  $<1.5 \times 10^9/L$  by the end of a two-week period (14 days) ([Section 8.2.4.9](#)).

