##### **Management**

*Mild Neutropenia* (two consecutive Absolute Neutrophil Counts  $\geq 1.0 \times 10^9/L$  and  $< 1.5 \times 10^9/L$ ):

Patients receiving deferiprone treatment who experience mild neutropenia (ANC  $\geq 1.0 \times 10^9/L$  and  $< 1.5 \times 10^9/L$ ) should continue treatment. The patient's ANC will be monitored every 2 days until resolution of the event, defined as two consecutive ANC  $\geq 1.5 \times 10^9/L$ . If the ANC remains  $\geq 1.0 \times 10^9/L$  and  $< 1.5 \times 10^9/L$  by the end of a two-week period (14 days):

- The patient will be withdrawn from the study and monitored until resolution of the event.
- The patient will be advised regarding protective isolation.
- The Investigator will notify ApoPharma Inc. by fax.
- The Investigator will examine patient the same day (if possible) including drug history and physical examination.

However, if the patient has a mild neutropenia and develops an infection, therapy must be interrupted immediately and neutrophil count must be obtained and monitored more frequently (every 2 days if ANC  $< 1.5 \times 10^9/L$ ) until resolution of the event, defined as two consecutive ANC  $\geq 1.5 \times 10^9/L$ . Patients should be advised to report immediately to their physician any symptoms indicative of infection such as fever, sore throat, and flu-like symptoms. In presence of confirmed fever and/or infection, they will be required to have their neutrophil counts tested as soon as possible and no later than 24 hours after the symptoms of infection are detected. Patients will be provided with an emergency services card with contact information, and the patient/legal guardian will be advised to carry this card at all times. Therapy with deferiprone can be initiated once all symptoms have been resolved and it is deemed safe by the Investigator.

Moderate Neutropenia (two consecutive Absolute Neutrophil Counts  $\geq 0.5 \times 10^9/L$  and  $< 1.0 \times 10^9/L$ ):

Patients receiving deferiprone treatment who experience moderate neutropenia (ANC  $\geq 0.5 \times 10^9/L$  and  $< 1.0 \times 10^9/L$ ) will immediately interrupt treatment, and the patient's ANC will be monitored every 2 days until resolution of the event, defined as two consecutive ANC  $\geq 1.5 \times 10^9/L$ . If the ANC remains  $< 1.5 \times 10^9/L$  by the end of a two-week period (14 days):

- The patient will be withdrawn from the study and monitored until resolution of the event.

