## CLINICAL STUDY PROTOCOL

STUDY CODE: LA38-0411

STUDY PROCEDURE	Baseline Phase				Treatment Phase			
	Screening/ Baseline	Baseline	Hematology Assessments 	Telephone Calls (Week 1, 2, 3)	Monthly Visits (Week 4, 8, 16, 20, 32, 36, 44, 48)	Quarterly Visits (Week 12, 40)	Semi-Annual Visit (Week 26)	End of Study / Early Termination Visit  (Week 52)
Quality of Life Questionnaire (SF-36/ Child Health Questionnaire)		X					X	X
Serum Ferritin		X				X	X	X
Liver MRI/LIC	X 						X	X
Cardiac MRI T2*	X 						X	X
Dose Calculation/Verify and adjust dose level		X			X	X	X	
Contact IVRS/IWRS		X			X	X	X	X
Dispense study medication		X			X	X	X	
Dispense Patient Diary Card		X			X	X	X	
Review and Collect Diary Card					X	X	X	X
Medical events/Adverse events	X	X		X	X	X	X	X
Concomitant medications				X	X	X	X	X
Transfusion information (if applicable) 			X		X	X	X	X
Return used and unused study medication					X	X	X	X

X- To do, V- To verify, R- To review

1. Hematology testing is to be done weekly up to Week 26 and biweekly thereafter.
2. Early Termination: if patient withdraws from the study prior to Week 52, the patient must be seen for an early termination visit.
3. These evaluations must be done within 14 days prior to baseline visit. Females of childbearing potential must be making use of an approved birth control method at least one month prior to starting study medication.
4. Results from these tests will be considered the baseline values.
5. Height will only be measured at screening/baseline, semi-annual and Week 52 visits.
6. These evaluations must be conducted within two months prior to starting study medication
7. Collect volume of blood that the patient received during the transfusion and the mean hematocrit of the packed red blood cell units transfused.

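### The protocol defines confirmed neutropenia for all patients but writes close re-counting only for deferiprone patients, so neutropenia may not be recorded comparably in the two arms

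*Protocol*

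**What the plan says.** **Definition.** Protocol 8.2.4.9 names neutropenia as the adverse event of special interest and grades it by confirmed ANC. The confirmation rule is: "An absolute neutrophil count (ANC) is confirmed as being less than a specified value if two consecutive counts (maximum 3 days apart) are both" below that value. If both counts are below 1.5 ×10^9/L but in different severity bands, "a third count will be required to determine the severity". Neither sentence names an arm.

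**Schedule.** Protocol 18.1, footnote 1, applies to both arms: "Hematology testing is to be done weekly up to Week 26 and biweekly thereafter". Section 5.4 gives each of these counts a window of ±3 days.

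**Close re-counting.**
- The mild category under Management in 8.2.4.9 opens "Patients receiving deferiprone treatment who experience mild neutropenia" and continues that the patient's "ANC will be monitored every 2 days until resolution of the event, defined as two consecutive ANC" values at or above 1.5 ×10^9/L.
- The moderate category has the same 2-day interval and the severe category daily follow-up. Both are worded for patients on deferiprone.
- Section 4.6 orders counts every 2 days with the condition "If the patient develops moderate neutropenia while on deferiprone". Its infection bullet also asks for counts every 2 days when ANC is below 1.5 ×10^9/L, and the only drug it names is deferiprone.
- Nothing equivalent is written for deferoxamine.

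**Analysis.** A secondary objective in Protocol 2.2 is "To evaluate the safety and tolerability of deferiprone vs. deferoxamine". Protocol 11.2.3 lists the frequency, severity and duration of adverse events as safety endpoints. The SAP table shells compare adverse events by preferred term between arms with Fisher's exact test (Tables 14.3.1.2 to 14.3.1.7). SAP 8.5 keeps laboratory values from unscheduled visits out of the summary tables. The SAP has no table of confirmed neutropenia.

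**The concern.** A definition that needs two counts within 3 days depends on someone taking an extra count. If extra counts are prompted in one arm and not in the other, the same fall in ANC can be confirmed, graded and timed differently by arm.

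Three features could carry this into the reported results. Investigators know the treatment. SAP 8.1 classifies each patient by the most severe event, and counting every 2 days gives more chances of catching a lower nadir than counting every 7 or 14 days. Duration is also measured on a finer grid where counts are closer together.

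At stake is the randomised estimate of excess neutropenia on deferiprone. Protocol 1 describes this as a confirmatory trial, and Protocol 1.4 says earlier studies included only a small number of patients with sickle cell disease. The likely direction is an overstated excess on deferiprone and an understated background rate on deferoxamine.

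**Working it through.** **1. The plan's nearest safety figures reproduce.** The chance of at least one event is 1 − (1 − p)^n.
- n = 300: 0.9977 at p = 2% and 0.9510 at p = 1% (stated: over 99% and over 95%).
- n = 213: 0.9865 and 0.8824 (stated: 98% and 88%).

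None of these is in dispute. They assume that every event is recorded, in either arm.

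**2. How often the schedule alone confirms a case.** Let consecutive counts be due P days apart and be taken a and b days from their due days, with a and b whole days from −3 to +3, all equally likely. The gap is P + b − a, over 7 × 7 = 49 combinations.
- Weekly, P = 7: gaps run from 1 to 13 days. A gap of at most 3 days needs a − b ≥ 4, which gives 3 + 2 + 1 = 6 combinations; 6/49 = 12%.
- Two-weekly, P = 14: gaps run from 8 to 20 days; 0/49.

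Clinic-visit counts might instead follow the ±7-day visit window in Protocol 5.6 to 5.8. For a visit count followed by a ±3-day weekly count, 24 of 15 × 7 = 105 combinations then lie 1 to 3 days apart in either order (23%). In the two-weekly phase the smallest gap is 14 − 7 − 3 = 4 days, so still none. These shares assume that the low count lasts until the next draw; shorter episodes lower them.

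**3. What the re-count instructions cover.** The headings for mild, moderate and severe neutropenia under Management already require two consecutive low counts. On that reading the 2-day and daily counts follow confirmation and do not supply it. The infection bullet in Protocol 4.6 has no such condition and would supply a second count within 3 days. No section expressly orders the confirming count in either arm.

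**4. Illustration of size.** The documents give no deferoxamine rate and no re-count rate. Assume the same true rate p in both arms, complete confirmation on deferiprone, and a fraction c confirmed on deferoxamine. With the SAP 3.2 interim arm sizes, expected confirmed cases are 142p and 71pc. The last column is the exact chance of Fisher p < 0.05 against deferiprone when there is no true difference.

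| p | c | Deferiprone | Deferoxamine | False signal |
|---|---|---|---|---|
| 6.2% | 1 | 8.8 | 4.4 | 1.3% |
| 6.2% | 0.5 | 8.8 | 2.2 | 8.5% |
| 6.2% | 0.12 | 8.8 | 0.54 | 34% |
| 3.1% | 1 | 4.4 | 2.2 | 0.4% |
| 3.1% | 0.5 | 4.4 | 1.1 | 1.1% |
| 3.1% | 0 | 4.4 | 0 | 3.4% |
| 1.7% | 0 to 1 | 2.4 | 0 to 1.2 | below 0.1% |

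The 6.2% and 1.7% are the pooled deferiprone figures for neutropenia and agranulocytosis in Protocol 1.2; 3.1% is half of 6.2%. At p = 3.1%, c between 0 and 0.5 gives an apparent excess of 3.1 − 3.1c, that is 1.6 to 3.1 percentage points. The table describes confirmed events, which are not what the SAP's adverse event tables count.

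**5. What the planned ANC outputs show.** They give means and changes by visit, low/normal/high shifts from baseline to the last assessment, and the proportion abnormal at each assessment. They rest on a schedule common to both arms. None shows the proportion of patients ever below 1.5, 1.0 or 0.5 ×10^9/L. An episode at Week 10 that resolves does not appear in the shift table.

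**The case against.** The strongest reply is that the planned comparison does not use confirmed neutropenia. Protocol 8.2.4.2 and SAP 8.5 make a laboratory abnormality an adverse event when it is clinically significant, in either arm and without a second count. A deferoxamine patient with a single ANC of 1.2 is unconfirmed, not unrecorded. The event table in Protocol 1.2 lists a decreased neutrophil count (7.3%) separately from neutropenia (6.2%), so a low count can be coded under another term.

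Several provisions also apply to both arms and could prompt a second count on deferoxamine: the third-count rule, review of results on receipt (5.4), testing within 24 hours of infection symptoms (4.6), and mandatory withdrawal for severe neutropenia (4.5), which obliges sites to apply the definition.

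These points stand, and they rule out two stronger readings. A reader might infer that deferoxamine cases will largely go unconfirmed. That holds only if investigators order no extra counts, which the documents do not say. A reader might also infer that the comparison is biased by a calculable amount. The documents do not support that, because recording does not require confirmation and the confirmation fractions above are assumptions.

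The reply does not restore comparability. Investigators hold a definition and close-count instructions aimed at one arm, they know the treatment, and severity and duration still depend on how often ANC is measured. The planned ANC tables are symmetric by schedule but omit the per-patient threshold result that would settle the question.

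**Conclusion.** The concern holds as a risk to comparability. Confirmation is defined for everyone, the common schedule rarely or never delivers it, close counting is written for deferiprone patients, and neither arm has an express instruction for the confirming count. The adverse event comparisons may therefore overstate the deferiprone excess.

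The size cannot be fixed from the documents. The 12% rests on whole-day deviations being equally likely within ±3 days and on the low count persisting. The illustrative excess rests on assumed rates and on complete confirmation in one arm only. Even under those assumptions, the main harm at 3.1% or below is a distorted estimate, with little chance of a false significant result. At 6.2% with little deferoxamine confirmation, a false signal becomes a real possibility. A neutropenia comparison that does not depend on re-testing can be had cheaply, so the SAP should include one.

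**What to change.** **SAP 8.1 and 8.5.** Add one table by arm giving the number and proportion of patients with any scheduled ANC below 1.5, below 1.0 and below 0.5 ×10^9/L. Use single counts from planned draws only, including scheduled draws done at local laboratories. Name this table as the primary between-arm comparison of neutropenia. Show separately, by arm, the confirmed events and the number of low counts that had a second count within 3 days, so that a reader can see whether re-testing differed.

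**Protocol.** Section 4.6 and the Definitions and Management parts of 8.2.4.9 must be reconciled, so that it is clear to whom the confirmation rule and the close-count instructions apply. How patients should be monitored is a clinical decision and is not proposed here. Any change comes late: the SAP projects that 213 patients will have finished or withdrawn by 30 November 2018, with 17 ongoing and enrolment on hold.

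**Cost.** One extra table from counts already collected. Single counts will include some transient dips, and patients who leave early contribute fewer scheduled counts, so the number of counts obtained in each arm should stand beside the proportions.
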